4.8.2 Switch Exclusion Criteria

Subjects in Group B may not switch to treatment with PEG-IFN if the answer to any of the following statements is "yes".

- Cirrhosis (see [Appendix 1](#))
- Subjects who have received any anti-HBV treatment within 6 months prior to switch baseline
- Positive test results within 6 months prior to switch baseline for HAV IgM Ab, anti-HCV Ab, anti-HDV Ab, or anti-HIV Ab
- Evidence of decompensated liver disease (e.g., Child–Pugh Class B or C clinical classification, see [Appendix 2](#) or *clinical evidence such as ascites or varices*) at switch baseline
- *Serum ALT >10 × the ULN at switch baseline. Reference range of the testing laboratory should be used*

- International normalized ratio > 1.5 at switch baseline
- Neutrophil count < 1.5×10^9 cells/L, platelet count < 90×10^9 cells/L, or hemoglobin < *lower limit of normal (LLN)* at switch baseline
- *Evidence of renal impairment*
- Evidence of severe illness or any other conditions or contraindications that would make the subject, in the opinion of the investigator, unsuitable for commencing PEG-IFN
- Clinically relevant abnormal thyroid function tests (TSH, FT3, FT4, TPO antibodies, and/or TBG) within 6 months prior to switch baseline
- Sexually active females of childbearing potential and sexually active males who are not willing to use reliable contraception during the switch treatment period and initial 24-week switch follow-up period
- Females of childbearing potential who have a positive urine or serum pregnancy test result within 24 hours of switch baseline

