Assessment/Procedure	Screen (days)	BL (days)	Principal Observation Period (weeks)				Initial Follow-up (weeks Post-End of Principal Observation Period)		Long-Term Follow-Up (years Post-End of Principal Observation Period)					
	-35 to -1	1	12	24	36	48 ^a	12 ^a	24 ^a	1 ^a	1.5 ^b	2	3	4	5
Urine or serum HCG pregnancy test (selected subjects) ^{c, d}	x													
Alfa-fetoprotein ^{e, h}	x													
Anti-HAV IgM, anti-HCV, anti-HIV, and anti-HDV ^h	x													
HBV genotype ^h	x													
Ceruloplasmin, A1AT, AMA, ANA, ASMA, ALKM1 ^h	x													
Hematology ^{f, i}	x	x	x	x	x	x		x						
Chemistry ^{f, i}	x	x	x	x	x	x		x						
Urinalysis ^{d, f, g}	x	x				x		x						
FT3, FT4, TSH ^{f, h}	x					x		x	x		x	x	x	x
TPO antibodies, TBG ^h	x													

- ^a Eligible subjects may switch at any time between Week 48 and 1 year following Week 48 at which time subjects will continue on the Switch Schedule of Assessments and Procedures.
- ^b By telephone.
- ^c For females of childbearing potential, a pregnancy test will be performed within 24 hours prior to baseline, and at any time secondary amenorrhea of more than 1 week occurs. *Result of baseline pregnancy test must be available prior to randomization and commencement of treatment.*
- ^d To be performed by local laboratory.
- ^e Subjects need to have serum alfa-fetoprotein assessed during the screening period to rule out hepatocellular carcinoma.
- ^f If there are clinically significant laboratory abnormalities, repeat no less frequently than every 2 weeks or as clinically indicated, with appropriate toxicity management, until they return to normal or baseline values.
- ^g Urinalysis to be performed via dipstick, with subsequent microscopic evaluation if positive for blood at the discretion of the investigator.
- ^h Parameter does not need to be repeated at re-screening if performed within 6 months prior to baseline, unless dictated by a change in the subject's medical condition or the parameter accounted for the original screen failure.
- ⁱ To be performed by a local laboratory in countries activated prior to April 2013, and by a central laboratory in countries activated after April 2013.

Table 3 Schedule of Assessments and Procedures—Group B (Untreated Control) (cont.)

Assessment/Procedure	Screen (days)	BL (days)	Principal Observation Period (weeks)				Initial Follow-up (weeks Post-End of Principal Observation Period)		Long-Term Follow-Up (years Post-End of Principal Observation Period)					

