Physical examination	x														x							
Symptom-directed physical examination		x	x	x	x	x	x	x	x	x	x	x	x	x								
Vital signs	x	x	x	x	x	x	x	x	x	x	x	x	x	x								
Weight ^d	x ^f	x	x	x	x	x ^f	x	x ^f	x	x ^f	x	x	x	x		x		x	x	x	x	
Height ^{d, e}	x ^f					x ^f		x ^f		x ^f		x			x		x	x	x	x		
Ophthalmology exam ^g	x ^j							x				x										
Urine or serum HCG pregnancy test (selected subjects) ^{h, i}	x			x	x	x	x	x	x	x	x	x	x	x								
Anti-HAV IgM, anti-HCV, anti-HIV, and anti-HDV ^j	x																					
ANA	x ^j							x				x										

^a Switch baseline will take place at the time of the final visit of the pre-switch schedule. Results from all switch baseline assessments must be available and subjects must meet all switch criteria prior to commencing PEG-IFN.

^b Or upon and following study treatment withdrawal.

^c By telephone.

^d Measurements must be taken using the same instruments in the same individual.

^e Using stadiometer and taking the mean of three readings.

^f Weight and height to be provided to IXRS.

^g By ophthalmologist (*pediatric ophthalmologist is recommended*) and including fundoscopic examination *with dilation*, visual acuity assessment, visual field testing (*confrontation test is recommended for younger children*), and color visual testing. Any subject who develops ocular symptoms should receive a prompt eye examination by an ophthalmologist and additional examinations as necessary.

^h For females of childbearing potential, a pregnancy test will be performed within 24 hours prior to switch baseline, and at any time secondary amenorrhea of more than 1 week occurs. *Result of baseline pregnancy test must be available prior to randomization and commencement of treatment.*

ⁱ To be performed by local laboratory.

^j Parameter does not need to be repeated at switch baseline if performed within 6 months prior to switch baseline, unless dictated by a change in the subject's medical condition.

Table 4 Schedule of Assessments and Procedures—Switch (PEG-IFN) (cont.)

Assessment/Procedure	Switch BL ^a	Treatment Period (weeks)												Initial Follow-up (weeks Post-End of Principal Observation Period)			Long-Term Follow-Up (years Post-End of Principal Observation Period)				
		SW 1	SW 2	SW 4	SW 8	SW 12	SW 18	SW 24	SW 30	SW 36	SW 42	SW 48 ^b	SW 4 ^b	SW 12 ^b	SW 24 ^b	SW 1 ^b	SW 1.5 ^{b,c}	SW 2 ^b	SW 3 ^b	SW 4 ^b	SW 5 ^b
Hematology ^{d,j}	X	X	X	X	X	X	X	X	X	X	X	X	X	X	X						
Chemistry ^{d,j}	X	X	X	X	X	X	X	X	X	X	X	X	X	X	X						

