Urinalysis ^{d,e,f}	X			X	X	X	X	X	X	X	X	X	X	X	X						
FT3, FT4, TSH ^d	X ⁱ					X		X		X		X		X	X	X		X	X	X	X
TPO antibodies	X ⁱ							X				X									
TBG	X ⁱ																				
Population PK ^g	X	X		X	X			X													
HBeAg, anti-HBe ^h	X ⁱ					X		X		X		X		X	X	X		X	X	X	X
HBV-DNA ^h	X ⁱ					X		X		X		X	X	X	X	X		X	X	X	X
HBsAg, anti-HBs ^h	X ⁱ					X		X		X		X		X	X	X		X	X	X	X

^a Switch baseline will take place at the time of the final visit of the pre-switch schedule. Results from all switch baseline assessments must be available and subjects must meet all switch criteria prior to commencing PEG-IFN.

^b Or upon and following study treatment withdrawal.

^c By telephone.

^d If there are clinically significant laboratory abnormalities, repeat no less frequently than every 2 weeks or as clinically indicated, with appropriate toxicity management, until they return to normal or baseline values.

^e Urinalysis to be performed via dipstick, with subsequent microscopic evaluation if positive for blood at the discretion of the investigator.

^f To be performed by local laboratory.

^g Specific sites. Blood samples should be collected for PK analysis during switch Weeks 1 and 24 at pre-dose (0 hour) and 24–48, 72–96, and 168 hours post-dose. Additional pre-dose samples should be collected at switch Weeks 4, 8 and 12 within 6 hours prior to PEG-IFN administration. The time of PEG-IFN administration on PK sampling days must be recorded on the eCRF.

^h Frozen for central processing.

ⁱ Parameter does not need to be repeated at switch baseline if performed within 6 months prior to switch baseline, unless dictated by a change in the subject's medical condition.

^j To be performed by a local laboratory in countries activated prior to April 2013, and by a central laboratory in countries activated after April 2013.

Table 4 Schedule of Assessments and Procedures—Switch (PEG-IFN) (cont.)

Assessment/Procedure	Switch BL ^a	Treatment Period (weeks)												Initial Follow-up (weeks Post-End of Principal Observation Period)			Long-Term Follow-Up (years Post-End of Principal Observation Period)					
		SW 1	SW 2	SW 4	SW 8	SW 12	SW 18	SW 24	SW 30	SW 36	SW 42	SW 48 ^b	SW 4 ^b	SW 12 ^b	SW 24 ^b	SW 1 ^b	SW 1.5 ^{b,c}	SW 2 ^b	SW 3 ^b	SW 4 ^b	SW 5 ^b	
Quantitative HBsAg and HBeAg ^d	x ^k					x		x		x		x			x							
Serum bank ^e	x					x		x		x		x			x	x	x		x	x	x	x
RCR plasma and RNA specimen	x					x		x				x			x	x		x	x	x	x	

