Adverse events	x	x	x	x	x	x	x	x	x	x	x	x	x	x	x	x	x ^f	x ^f	x ^f	x ^f	x ^f	x ^f
Concomitant medications (including for CHB ^g)	x	x	x	x	x	x	x	x	x	x	x	x	x	x	x							
Concomitant medications for CHB only ^g																	x	x	x	x	x	x
Subject study drug diary		x	x	x	x	x	x	x	x	x	x	x										
Dispense study drug	x			x	x	x	x	x	x	x	x											
Compliance	x	x	x	x	x	x	x	x	x	x	x	x	x	x	x	x	x	x	x	x	x	x
Neuro-Psychiatric Questionnaire ^h	x					x		x			x		x									
Liver biopsy ⁱ	x																					
Ultrasound ⁱ	x																					
Liver elastography ^j													x			x			x			

^a Switch baseline will take place at the time of the final visit of the pre-switch schedule. Results from all switch baseline assessments must be available and subjects must meet all switch criteria prior to commencing PEG-IFN.
^b Or upon and following study treatment withdrawal.
^c By telephone.
^d Frozen for central processing.
^e Sample to be retained frozen at site in the event that any tests need to be repeated. From RCR-consenting subjects, they also may be used for exploratory HBV biomarker analyses (DNA and/or non-DNA).
^f During the 5-year follow-up period, only persistent AEs initially reported prior to follow-up Week 24, new-onset SAEs *and* non-serious AEs of special interest related to PEG-IFN, and deaths will be collected.

Table 4 Schedule of Assessments and Procedures—Switch (PEG-IFN) (cont.)

- ^g Concomitant medications for CHB include licensed or investigational immunomodulatory or antiviral therapy, ursodeoxycholic acid, and herbal, botanical and other agents (e.g., ursodeoxycholic acid) that are traditionally used for chronic HBV disease.
- ^h Not required for children <7 years of age.
- ⁱ Either a liver biopsy performed within 2 years prior to switch baseline to exclude cirrhosis, OR clinical, laboratory, and ultrasound data within 6 months prior to switch baseline which together exclude cirrhosis.
- ^j Subjects in site-specific liver elasticity sub-study only.
- ^k Parameter does not need to be repeated at switch baseline if performed within 6 months prior to switch baseline, unless dictated by a change in the subject's medical condition.

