5.3 CLINICAL ASSESSMENTS AND PROCEDURES

A baseline visit will be performed, and for subjects in Group A and Group C all baseline assessments and procedures must occur prior to administration of the first dose of PEG-IFN. *The first dose of PEG-IFN should be administered at the baseline visit.* Subjects will subsequently be seen for evaluation at the following timepoints:

Group A and Group C

- During treatment period: Weeks 1, 2, 4, 8, 12, 18, 24, 30, 36, 42, and 48

Pegylated Interferon alfa-2a—F. Hoffmann-La Roche Ltd
Protocol YV25718, Version E

69

- During initial 24 weeks of follow-up: follow-up Weeks 4, 12, and 24 post-*end of treatment*
- During extended long-term follow-up: Years 1, 1.5, 2, 3, 4, and 5 post-*end of treatment*

Group B—Non-Switch

- During principal observation period: Weeks 12, 24, 36, and 48
- During initial 24 weeks of follow-up: follow-up Weeks 12 and 24 post-principal observation period
- During extended long-term follow-up: Years 1, 1.5, 2, 3, 4, and 5 post-principal observation period

Group B—Switch

- During principal observation period: Weeks 12, 24, 36, and 48*
- During initial 24 weeks of follow-up: follow-up Weeks 12* and 24* post-principal observation period
- During extended long-term follow-up: Year 1* post-principal observation period
- During switch treatment period: Weeks 1, 2, 4, 8, 12, 18, 24, 30, 36, 42, and 48
- During initial 24 weeks of switch follow-up: switch follow-up Weeks 4, 12, and 24 post- *end of treatment* period
- During extended long-term switch follow-up: Years 1, 1.5, 2, 3, 4, and 5 post- *end of treatment* period

*Subjects may switch at any time between Week 48 and 1 year following Week 48. Switch baseline will take place at the time of the final visit of the pre-switch schedule. Results from all switch baseline assessments must be available and subjects must meet all switch criteria prior to commencing PEG-IFN.

The extended long-term follow-up visit at Year 1.5 will be by telephone.

For assessments and procedures required at each visit refer to [Table 2](#) to [Table 4](#).

For visits up to and including Week 48, the visit window is ± 3 days.

For visits after Week 48 and up to and including follow-up Week 24, the visit window is ± 7 days.

For visits after follow-up Week 24, the visit window is ± 28 days.

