5.3.2 Safety

Safety assessments will include symptom directed physical examination, vital signs, growth, neuro-psychiatric questionnaire (PEG-IFN-treated subjects only, post-baseline), review of concomitant medications, reported AEs and specified safety laboratory assessments of hematology, clinical chemistry, thyroid function, and urinalysis. Additional safety assessments will be determined from tabulations of dose adjustments and premature withdrawals from treatment for safety or tolerability reasons.

All subjects need to have an ophthalmological examination (*consisting of fundoscopic examination with dilation, visual acuity assessment, visual field testing (confrontation test is recommended for younger children), and color visual testing*) by an ophthalmologist (*pediatric ophthalmologist is recommended*) within 6 months prior to baseline. *During the study*, subjects treated with PEG-IFN will receive *additional* ophthalmological examination as per the schedules in Table 2 and Table 4. Any subject who develops ocular symptoms should receive a prompt eye examination by an ophthalmologist and additional examinations as necessary.

For females of childbearing potential, a pregnancy test will be performed within 24 hours prior to baseline or switch baseline. This could be performed at the baseline visit, provided that the result is available prior to randomization and commencement of treatment. Pregnancy testing will also be performed at any time secondary amenorrhea of more than 1 week occurs. In addition, subjects treated with PEG-IFN will have pregnancy tests performed as per the schedules in Table 2 and Table 4.

Measurements of growth must be taken using the same instruments in the same individual. A stadiometer with mean of three readings should be used for height measurement. For Group A and C subjects, at Weeks 12, 24, and 36, and for switch subjects at switch baseline, switch week (SW)12, SW24, and SW36 the investigator or

designee will provide IXRS with the subject's height and weight so that the BSA and dose can be provided.

Height will be collected from consenting biological parents. This information may be entered directly onto the eCRF and the eCRF may be considered as the source document.

During the extended long-term follow-up period, only the following safety data will be collected:

- Persisting AEs initially reported prior to follow-up Week 24 (including neurological and psychiatric events)

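### Switch arm: the 24-hour pregnancy test is tied to switch baseline, yet the first PEG-IFN dose must wait for results and can come later, with no repeat test

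*Protocol*

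**What the plan says.** **Timing of the test.** Protocol Table 4 (Switch schedule), footnote h, reads: "For females of childbearing potential, a pregnancy test will be performed within 24 hours prior to switch baseline". Section 4.8.2 excludes a girl with a "positive urine or serum pregnancy test result within 24 hours of switch baseline". Section 5.3.2 uses the same reference point: "a pregnancy test will be performed within 24 hours prior to baseline or switch baseline". The SAP repeats the footnote in Appendix 2, Table 3. Section 7.3 says only that a test precedes baseline and switch baseline. None of these places refers to the first switch dose.

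**Condition for dosing.** Section 5.3 and Table 4 footnote a say: "Results from all switch baseline assessments must be available and subjects must meet all switch criteria prior to commencing PEG-IFN". Section 4.8.2 sets limits at switch baseline for ALT, INR, neutrophils, platelets and hemoglobin. In Table 4, hematology and chemistry carry no six-month reuse footnote. Footnote j sends them to a local laboratory in earlier-activated countries and has them run "by a central laboratory in countries activated after April 2013".

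**Signs that dosing is expected at switch baseline.** Table 4 marks "Dispense study drug" in the Switch BL column and shows no separate first-dose visit. Table 7 (PK sub-study) places the pre-dose and post-dose samples under switch baseline, with the 168-hour sample falling at the Week 1 visit.

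**Groups A and C.** Section 4.3 dates their test to within 24 hours of baseline, and Section 5.3 has the first dose given at the baseline visit.

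**The concern.** A pre-treatment pregnancy test is meant to show that a girl is not pregnant when she is first exposed. Groups A and C have their eligibility results from screening, so test and dose both belong to the baseline visit. The Switch arm combines eligibility testing and baseline in one visit but keeps a test rule built for the other sequence. Footnote h even asks for the result before randomization, although nobody is randomized at switch.

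If dosing has to wait for blood results, the test ages during the wait. The text caps neither the wait nor the age of the test, and it requires no repeat unless menstruation is more than a week overdue. At stake is a first exposure in early pregnancy, in a trial whose Section 7.3 asks for extreme care to avoid it and notes that no adequate controlled interferon studies in pregnancy exist.

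**Working it through.** The plan gives no figure to reproduce. The check compares the rules and then counts days.

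**Step 1: what each rule is tied to.**

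| Item | Groups A and C | Switch arm |
|---|---|---|
| Pregnancy test | within 24 h of baseline (4.3) | within 24 h of switch baseline (4.8.2, 5.3.2, Table 4 footnote h) |
| Eligibility bloods | at screening, before baseline (Table 5) | hematology and chemistry at switch baseline (Table 4) |
| First dose | at the baseline visit (5.3) | once all switch-baseline results are in (5.3, Table 4 footnote a) |
| Stated maximum from test to first dose | in effect, same visit | none |
| Next scheduled pregnancy test | Week 4 (Table 2) | SW4 (Table 4) |

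**Step 2: must the dose ever wait?** Yes, wherever hematology or chemistry is not reported on the day. The ALT, INR and blood-count criteria refer to values at switch baseline, and no reuse allowance covers them. A central laboratory makes a same-day result less likely. A site with same-day local results, and any other required tests already in hand, need not wait.

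**Step 3: does any text close the gap?**
- Footnote h and Section 5.3.2 require the result to be known before treatment. That concerns availability, not age.
- The one-year offer ("Eligible subjects may switch at any time between Week 48 and 1 year following Week 48") limits when a child may switch, not the time from test to dose.
- The amenorrhea rule triggers a test only after more than one week.
- Table 3 schedules no pregnancy test for Group B after screening, so the switch-baseline test is the only scheduled one before dosing.

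**Step 4: age of the test at first dose.** Let W be the wait in days from switch baseline to first dose. The documents give no value, so W is an assumption. The test may be up to 1 day old at switch baseline, so its age at first dose is at most 1 + W days.

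| Assumed W (days) | Maximum age at first dose (days) |
|---|---|
| 0 | 1 + 0 = 1 |
| 1 | 1 + 1 = 2 |
| 7 | 1 + 7 = 8 |
| 14 | 1 + 14 = 15 |

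**Step 5: what is specific to the Switch arm.** In Groups A and C the next scheduled test is at Week 4 (day 28, window ±3 days), at most 1 + 28 + 3 = 32 days after the pre-dose test. In the Switch arm, with weeks counted from the first dose, the same interval is 32 + W days, or 39 days for W = 7. Weekly doses on days 0, 7, 14 and 21 come before the Week 4 test in every treated arm. The Switch wording therefore adds only W.

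**The case against.** The strongest reply is that switch baseline is meant to be the dosing day. Drug is dispensed then, the IXRS supplies the dose from height and weight taken then, and Table 7 works only if the first dose falls then. On that reading, a test within 24 hours of switch baseline is a test within 24 hours of the dose. This shows what the schedule assumes, and it stands as evidence of intent. It does not remove the explicit bar on starting before results arrive. The two instructions conflict, and a site that obeys the bar can give the first dose on an older test.

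The reply also notes other safeguards: willingness to use contraception is a switch condition, a missed period prompts a test, Section 7.2.4 requires a pregnant girl to stop the drug at once, and pregnancy tests during treatment are accepted at 4- to 6-week intervals. These keep the risk small, and a test about a week old is well inside those intervals. But the tests during treatment follow exposure that has already begun. The pre-dose test is there to prevent first exposure, and the plan's own standard for that is 24 hours.

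A reader might infer three stronger things that the documents do not support:
- **The four doses before SW4 are a Switch-arm harm.** They are not; Groups A and C have the same gap.
- **Contraception lapses for most of the switch window.** The entry rule in 4.3 names the initial 24-week follow-up, and the switch rule in 4.8.2 names switch treatment and its 24-week follow-up. This could be read as leaving 52 − 24 = 28 of 52 weeks uncovered. That counts calendar weeks and says nothing about when children switch. Switch baseline falls at the last pre-switch visit, and after follow-up Week 24 only Year 1 remains within the window. Section 7.3's instruction also applies throughout the study.
- **A long wait or a definite count of girls can be stated.** No laboratory turnaround, sex split, share of childbearing potential or switch rate is given.

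**Conclusion.** The point holds as a conflict in the text with a small safety consequence. The pregnancy test is tied to switch baseline, the first dose is tied to the return of all switch-baseline results, and the schedule tables assume that both happen on one day. Where they do not, PEG-IFN can be started on a test older than 24 hours, with no cap and no required repeat.

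The excess age equals the wait. If that is 0 to 7 days (an assumption), the test is up to 1 to 8 days old, against at most 1 day in Groups A and C. Group B is about 48 to 53 children (145/3 = 48.3; 160/3 = 53.3 if nobody enters Group C). Only girls of childbearing potential who switch and have to wait are concerned, and that number cannot be derived from the documents. They do not support a claim that any pregnancy would be missed. The primary A-versus-B analysis is unaffected, since it counts any Group B child who switches before its endpoint as a non-responder. Priority: minor safety clarification.

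**What to change.** In protocol Sections 4.8.2 and 5.3.2 and Table 4 footnote h, and in the SAP copy (Appendix 2, Table 3, footnote h), require a negative local urine or serum pregnancy test within 24 hours before the first switch dose, repeated if dosing is not on the day of switch baseline. Align Section 7.3, and drop the reference to randomization from the Switch footnote.

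Optionally, add a note to Table 4 that drug is dispensed on the first-dose date and that SW weeks are counted from it. This would settle which day starts the Switch schedule, but the pregnancy safeguard does not depend on it.

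The cost is a few wording changes and, for some girls, a repeat local test with a short return visit. Table 4 already assigns the test to the local laboratory, so the change should add little or no delay to dosing.
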